### **Study Coordination**

The Division of Infectious Diseases at the University of Wisconsin School of Medicine and Public Health is the coordinating center for this study.

Investigators from numerous academic departments at UW-Madison and Tulane University will collaborate to refine study methodologies and adapt data collection and laboratory infrastructure during the fall of 2017, with a goal of commencing recruitment of subjects in January 2018.

Investigators will also participate in national working groups as part of a multi-site collaborative agreement including researchers in other states and Scientific Staff from the National Institute on Drug Abuse.

## Study Phases

Phase 1 (UG3) September 2017 – August 2019
 
Study activities
 
 
• Creation of working groups
 
• Building stakeholder support in 6 target communities
 
• Client survey and seroprevalence study in syringe service programs
 
• Community needs assessment
 
	
Phase 2 (UH3) September 2019 – August 2023
 
Study activities
 
 
• Development of Prevention Case Management Protocol
 
• Enrollment of syringe service program clients in Prevention Case Management Program at 3 Vivent Health offices
 
• Adaption of A-CHESS mobile health application (2021 Pilot).
 
• Virtual Prevention Navigation Implementation Cohort Study (during COVID-19 Pandemic)
 

Additional Phase 1 Activities (UG3) February 2022 – December 2023
 
Study Activities
 
 
• Link UG3 data with several registries from the WI Department of Health Services to ascertain longitudinal outcomes of interest during the COVID-19 pandemic
 
• Quantify rates of COVID-19 infection, testing, vaccination, and mortality from DHS data
 
• Quantify fatal overdose rates and nonfatal overdose hospitalization rates
 
• Quantify hepatitis A and B vaccination prevalence
 
	

## Phase 2 (UH3) Objectives

[figure not shown]
Participants in the intervention will undergo a 12-week intensive multilevel harm reduction case-management intervention geared towards coordinating referrals to reduce substance use disorder and increase engagement in the substance use disorder care cascades, and reduce vulnerability to HIV, STIs, and HCV and increase in engagement in the HIV, STI, and HCV care cascades. As shown in Figure 3, participants in the intervention arm will work with Prevention Navigators to undergo a risk assessment and identify problems that they will create goals to achieve. Each session after that will

be used to review the needs assessment and goals. During their last meeting, participants and prevention navigators will develop a discharge plan that will enable the participant to work on their goals on their own.

***COVID-19 Response and Amended Intervention.*** Wisconsin's Shelter in Place mandate has statewide closure effects, including the limiting of services delivered by Vivent Health, our main community partner. To best respond to this crisis and help PWID in rural WI, we will adjust our prevention navigation model to a virtual, COVID-19 risk related navigation for a short period of time (through Sep 2020).

Participants enrolled in the COVID-19 virtual navigation study will work with a navigator 4 times over the course of one month (1x/week) to reduce the risk of HIV, HCV, and overdose during this especially difficult time. Navigation will be focused on crisis response, safe drug seeking and sharing behaviors, at home HIV and HCV testing, overdose risk reduction, safe housing, stable food sources, and other relevant topics for PWID during the pandemic. After a trial of this model (ending Sep 2020), we will resume the original UH3 model (3 month intervention, and baseline, 3-month, and 6-month assessments) in a virtual format.

**Figure 3. Phase 2 (UH3) Study Flow**

### 3.0 SELECTION OF SUBJECTS

In preparation for this study, our team analyzed WI county-level data reflecting various aspects of the opioid epidemic to (1) understand geographic heterogeneity of opioid injection and its consequences in order to prioritize communities in greatest need of prevention services; (2) build capacity to monitor changes in opioid-related disease burden over time on a state-wide level; and (3) establish a framework to assess the impact of the community response model in counties served by the new model in comparison to those not served. In Table 4, we list the 6 counties we have selected as high-priority candidates for implementation of the Client-Centered Prevention Home model. They were

chosen because county-level data indicate a high burden of opioid injection and HCV infection, and because they are located in close proximity to a Vivent Health prevention office that could feasibly deliver services to the majority of residents.

Table 4. County-level data describing opioid epidemic in Vivent Health syringe service program.

Variable	Douglas County†	Eau Claire County†	Marathon County†	La Crosse County	Outagamie County	Brown County
HCV cases in ages 15-29 (per 100,000)	156.1	92.7	92.7	72.0	68.5	60.0
Opioid-related hospital visits (per 100,000 pop.)	205	79.9	48.7	83.8	67.4	70.8
Opioid prescriptions filled (per 1,000 pop.)‡	968.3	745.2	801.4	753	649.1	760.9
Percent of opioid prescriptions >90 MME daily‡	6.2	4.3	5.6	6.3	7.4	4.7
Syringes distributed by Vivent SSP in 2016 Q3	64,426	53,867	49,261	53,567	48,807	46,317

† Expected UH3 implementation site based on preliminary data (subject to change); ‡ Data obtained from WI Prescription Drug Monitoring Program

In the first phase of the study, we identified sufficient resources to ensure the feasibility of our proposed intervention in 5 of the 6 counties we have studied, and have selected 3 service regions for which the intervention will be ideally suited. The 3 study sites include La Crosse County, Marathon County, and Brown County.

In addition to confirming there are sufficient resources in the study areas, our research showed that the 3 selected communities differ from each other in notable ways, which will provide opportunities to study how implementation strategies may differ in varying contexts. For example, Brown County was unique in that the RDS survey engaged a much higher than expected number of Native American respondents. Respondents in Brown County also more commonly listed heroin as their “drug of choice,” while respondents in all other sites indicated methamphetamine was their preferred drug.

**COVID-19 Response and Amended Intervention.** In response to the national crisis, and to best serve PWID in rural WI, we will recruit subjects in our 3 intervention sites (Brown, Marathon, and La Crosse Counties). Additionally, we will be resampling participants who were enrolled in the UG3 phase of the study and who have given permission to be contacted about future research opportunities. Each navigator will have a case load of no more than 15 participants at one time throughout the course of this pilot. Once we have concluded the pilot in Sept 2020, we will resume aim 3 procedures.

## 4.0 REGISTRATION PROCEDURES

### Participant recruitment for Aim 1 (UG3 Phase).

Using a cross-sectional study design, we will enroll 1,200 people who inject drugs to get high and live in rural communities. Based on the volume of syringes distributed in 2016 at the six rural Vivent Health offices listed above, we anticipate enrolling 200 individuals at each site.

**Eligibility screening and enrollment of seeds.** Individuals will be eligible for enrollment if they are 15 years of age or older, have injected any drug to get high in the past 1 month, and reside in a rural community. Rural residence will be determined by ZIP code, which will be programmed in the screening instrument on REDCap. The system will classify the ZIP code as rural if the ZIP Code RUCA Approximation is >4 or the participant lives in a catchment ZIP code for the SSP.

A research assistant will screen clients for eligibility, either on site at Vivent Health or by phone. Vivent Health staff will notify clients of the opportunity to speak with research staff by phone if they

report living in a rural community, are 15 or older, and are actively injecting drugs. To minimize the involvement of Vivent Health staff in the screening process at sites where having Vivent Health staff engaged in research would interfere with routine prevention activities, we have developed a flexible screening process that can be done without the involvement of Vivent Health staff. At certain sites, Vivent Health staff may become engaged in research and fulfill the research assistant role for the purpose of screening, if the agency determines this is the best strategy for managing the flow of clients and study participants. Specifically:

1. As a matter of routine (i.e. independently of the study), syringe program staff collect the following information from clients: Age, zip code of residence, whether the client is actively injecting drugs, whether they are interested in referrals to drug treatment. Staff members also participate in several outreach testing events that are outside of the SSP centers, while testing for HCV and HIV at these events, staff collect information on age, zip code of residence, and whether the client is actively injecting drugs. During the study enrollment period, staff will notify clients of the opportunity to participate in the study if they report that they inject drugs, are 15 years of age or older, and reside in one of the targeted rural zip codes. Among those in testing events, SSP staff will pass along information telling the participant that they may be eligible to participate in the study. We have hired research staff to be on site who will help in screening and enrollment into the study.
2. Questionnaire by telephone. The screening questionnaire has been uploaded as part of the application.
3. If clients are determined to be eligible, then the research staff will collect their name and date of birth, and assign them a study ID number. They will then provide detailed information about the study procedures by reading the consent document. Copies of the consent document will be available in the private room at the Vivent Health prevention office, so that the client can read along and ask questions. Among participants recruited from outreach events, UW research staff will provide them the consent document and go over the study procedures in detail.
4. If the client agrees to participate, they will write down their assigned study ID and end the phone call. They will then notify the SSP staff that they have agreed to participate. SSP staff will direct them to the study computer, where they will complete the study questionnaire using the ACASI interface. The first step of the computerized questionnaire will be to review the full text of the consent document and to submit their electronic signature and study ID number, which will be stored with the study data. In alternative settings such as outreach events where internet connectivity is not reliable, a paper version of the consent form will be signed and securely stored by a research assistant before proceeding with any study procedures.

### **Participant recruitment for Aim 2 (UG3 Phase).**

The research team will conduct individual elicitation interviews with SSP clients, SSP staff, and local professionals involved in providing prevention and treatment services to people who use drugs in each of the 6 selected communities. A more rigorous approach to quantitatively assess barriers for medical providers, we will conduct a mail-based and email survey among 1,500 family medicine providers.

SSP staff, comprised of prevention specialists in the Vivent Health participating field offices, will be the points of first contact in each community. We have developed a semi-structured interview guide that will elicit staff perceptions about the target population, and the availability of prevention resources and health services. We will use these interviews as a starting point to collect names of providers and local agencies that provide services to people who inject drugs. This will allow us to build a referral network for provider interviews (Aim 2b), and to complete the local needs assessment.

A quantitative assessment of provider-level barriers will be conducted via a mail and email based survey among family medicine providers in WI in order to characterize barriers to optimal care and investigate opportunities to reduce health disparities among people who inject drugs (PWID). We will survey approximately 1,500 physicians specializing in family medicine who have a practice location in Wisconsin, as identified through an electronic database purchased from SK&A. To make specific comparisons among providers who have adopted office-based buprenorphine treatment (OBBT) in their primary care practice to those who have not, we will use a case-control study design, matching providers who have received a DEA waiver to prescribe buprenorphine to up to 2 non-waivered providers who practice in the same county. Cases have been identified through the Substance Abuse and Mental Health Services Administration's (SAMHSA) website. SAMHSA's database will be crosschecked by internet searches and phone confirmation to ensure that each provider is still practicing at reported location. We theorize that providers who have adopted office-based buprenorphine treatment have general awareness of the epidemic, and understanding barriers they face may be imperative. Controls (non DEA-waivered providers) will be drawn from the SK&A database. To achieve the target sample size of 1,500 providers, additional family medicine physicians will be sampled from the database, with priority given to providers practicing in the rural counties targeted in the parent study.

SSP clients will be recruited for individual-level interviews (Aim 2c) among participants who consent to participate in the client survey and seroprevalence study, described in Aim 1. Clients who participate in the cross-sectional study described above will be systematically invited (e.g., every nth person) to also participate in a qualitative interview. We anticipate conducting qualitative interviews with 5% of the cross-sectional sample (n=60) divided among the 6 counties. Additional interviews will be conducted if warranted by the data but a sample size of 30-50 is usually sufficient to achieve saturation and redundancy, a marker of sufficient sample size.

### **Participant recruitment for Aim 3 (UH3 Phase, 2019-2021).**

Based on preliminary data, burden of opioid-related illness, and familiarity with supportive local stakeholders, we selected La Crosse County, Marathon County, and Brown County as the implementation sites for this study. Eau Claire, Douglas, and Outagamie Counties will serve as the

nonintervention sites, where participants will receive services as usual. In the fall of 2019, 3 full-time Prevention Navigators were hired and trained to conduct the intervention. Participants in this phase of the study will be recruited into one of two groups, Prevention Navigation, or usual services. Beginning in year 3, SSP clients at the 6 selected Vivent Health sites will be notified about the study by prevention specialists or SSP staff if the client 1) tests for HCV or HIV at the SSP, 2) inquires about services that may be in the prevention home through casual conversation, 3) the client engages in naloxone training, 4) through posted materials of the availability of new resources for improving prevention services and linkages to treatment in the SSP and community offices, 5) recruit through flyers and posted materials in the SSP and local community resource offices, and public areas, 6) through Vivent Health Facebook advertisements, 7) through our study website listed on our flyers, and/or 8) through respondent-driven sampling (RDS). Upon the completion of the first two attended Prevention Navigation sessions,

participants will be given a referral coupon and asked to refer one eligible peers per coupon to participate in the study. Vivent Health will dispense coupons that have been prepared by UW research staff. SSP clients at the nonintervention sites will be recruited at the time the Vivent Health staff member assists them with regular exchange services. Nonintervention sites will aim to enroll about one participant every-other week.

[figure not shown]
[figure not shown]

Figure 5. Parallel crossover (wait-list control) and cross-site study design

**Eligibility screening and enrollment at baseline.** Individuals will be eligible for enrollment if they are 18 years of age or older, have injected any drug to get high in the past 1 month, and reside in a rural community. All persons who access services at the northern Wisconsin SSPs will be considered rural community members, so long as they reside in the state of Wisconsin. County of residence and zipcode will be collected, stored in the participant file, and recorded in REDCap.

Among nonintervention sites, eligibility criteria will be the same as intervention sites, with the exception of allowing Minnesota residents to participate in the Douglas County office.

At intervention sites the PN will administer the screening questionnaire in person or over the phone with the client. If the PN is not available, the client may answer the screening questionnaire on their own and immediately validate their answers with the PN before eligibility is determined (not applicable if virtual). Eligibility requirements will not be listed or shared with the clients. The screening questionnaire has been uploaded as part of the application. If the PN is unavailable, Vivent Health SSP staff will also be research trained and able to administer the screening questionnaire in person or over the phone.

If clients are determined to be eligible, then the research staff will collect their name and date of birth, and assign them a study ID number. They will then provide detailed information about the intervention, study procedures, and the consent document.

If the client agrees to participate, they will be read a verbal consent script over the phone, by video conference, or in-person by the prevention navigator, SSP staff, or UW staff. They will be required to answer T/F questions regarding the consent before giving verbal consent. Participants will fill out a locator form at this time to help SSP staff contact the participant for follow up visits.

Rapid testing for HIV and hepatitis C will be conducted by Vivent Health SSP staff, using standard procedures determined by the agency that are independent of the research protocol. The data collection forms used by the SSP staff will be shared with the research team in order to retrieve specific data elements needed for the study. Study forms will be securely transmitted to researchers after each research assessment.

Clients at the nonintervention sites who are determined to be eligible after SSP staff administer the screening questionnaire will have their name and date of birth collected and assigned a study ID number. The SSP or UW staff member will go through the study procedures and read a verbal consent script over the phone, by video conference, or in-person. They will be required to answer T/F questions regarding the consent before giving verbal consent. A locator form will be filled out at this time. Rapid testing for HIV and hepatitis C will be conducted by the SSP staff member using the same standard procedures as above. The data collection forms will again be shared with the research team securely after each research assessment.

All clients who are determined to be eligible will have a SSP or UW staff member go through the ACHESS specific activities (surveys and option activities) and read a verbal consent script over the phone, by video conference, or in-person. The participant will be required to provide verbal consent.

**COVID-19 Pilot Intervention.** Participants will be recruited to the virtual prevention navigation implementation pilot program through three avenues.

- 1) Participants who participated in phase 1 and consented to future contact will be recruited for the study
- 2) Clients who access current SSP services will receive a flyer in their safe injection supply bags with contact information to call if interested in the study
- 3) SSP staff may engage clients about the study if a client calls into the SSP asking for services

Participants will be eligible for enrollment if they are 18 years of age or older, have injected drugs in the past month, reside in a rural WI community, and can speak and understand the English language. Clients will speak with the Prevention Navigator to determine eligibility, consent to the study, and schedule their first navigation session. If the client agrees to participate, their name, DOB, county and zip code of residence, and phone number will be collected. Navigators will have a case load of no more than 15 participants at one time to ensure workload is manageable, with a final recruitment

number of n=108 intervention participants and n=108 control participants. Navigators may take down a client's phone number, per Vivent Health policy, in order to contact the individual when spots open.

We will pause recruitment for our originally proposed UH3 protocol until at least Sep 2020 when the pilot has ended.

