**Survey and needs assessment.** The primary source of data collection in all three groups of the study will be from the ACASI questionnaire, administered at 0 months (baseline), 3 months, and 6 months from enrollment. All surveys will be administered on a tablet using the ACHESS application, by the participant accessing the survey in ACHESS on their smartphone or web browser on their own time, or over the phone. The data will be securely stored at UW-Madison and erased from the tablet if

applicable. The survey will consist of multiple choice questions designed to efficiently assess drug use history, access and utilization of prevention services, readiness for intervention, and injection related risk behaviors. The final survey a participant takes will include exit questions to help us evaluate and improve the program. Participants enrolled in the intervention between February 1, 2023 and March 31, 2023 will complete the baseline and 3 months ACASI questionnaire only.

**ACHESS.** All participants will complete study assessments using the ACHESS application. ACHESS can be accessed by downloading the application to a smartphone or via a web browser. Participants may also take part in optional non-research activities within the ACHESS app. These activities include: 1) posting on discussion boards, 2) utilizing the private message function to communicate with study staff or other participants, 3) viewing local community resources and their contact information, 4) viewing and saving motivational quotes of the day and logging thoughts of gratitude, and 5) accessing study staff contact information.

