**1.7. Study design.** In order to measure the impact of the Client-Centered Prevention Home we will prospectively assess the 12-week intervention by measuring outcomes at baseline, 3-months, and 6-months. We will target participants who engage in syringe services at Vivent Health and may be interested in additional services that may be offered in our multilevel harm reduction intervention. At intervention sites, the Prevention Navigator will engage prospective clients by screening them for the study, having the participant sign the consent form and performing baseline assessments along with rapid testing for HIV, HCV, and syphilis. Using the same infrastructure used in the UG3 phase, a second group of controls will be enrolled at the three non-intervention sites. Syringe service program staff at the non-intervention sites will recruit participants for baseline, 3-month, and 6-month assessments during the two year study period.

The health-related goals for PWID in the context of this study are multi-faceted, reflecting the heterogeneous needs of this vulnerable population. Accordingly, there is not a single, primary outcome which can be measured to evaluate the impact or effectiveness of the intervention. We therefore have proposed a study design that allows us to evaluate the influence of prevention navigation on progress toward a number of health goals. Because no single study design can account for all of the biases inherent in a non-randomized, multi-county intervention trial, we have proposed 2 different types of comparisons in our evaluation strategy:

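### Entry into the two Aim 3 groups is not shown to be parallel, and comparison (B) has no stated adjustment for readiness or syringe-service use before navigation

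*Combined protocol and SAP*

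**What the plan says.** **Routes.** Section 4.0 (Participant recruitment for Aim 3) opens its list for all six sites: "SSP clients at the 6 selected Vivent Health sites will be notified about the study by prevention specialists or SSP staff if the client" meets one of the listed conditions. The eight routes are HCV or HIV testing, asking about services ("inquires about services that may be in the prevention home through casual conversation"), naloxone training, "posted materials of the availability of new resources for improving prevention services and linkages to treatment in the SSP and community offices", flyers, Facebook advertisements, the study website and respondent-driven sampling.

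**Coupon.** The same section sets when the peer route opens: "Upon the completion of the first two attended Prevention Navigation sessions", and then "participants will be given a referral coupon and asked to refer one eligible peers per coupon to participate in the study". Appendix 1, Section 1.4 states that the three control offices will not provide navigation.

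**Controls.** Section 4.0 then says that "SSP clients at the nonintervention sites will be recruited at the time the Vivent Health staff member assists them with regular exchange services".

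**Peer payment.** Section 9.0 (Incentives, Aim 3) gives participants $10 for each eligible peer who enrols, without naming a group.

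**Target population.** Appendix 1, Section 1.7 describes people who use the syringe service and "may be interested in additional services that may be offered in our multilevel harm reduction intervention". The sentence comes before the description of either type of site.

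**Measurement and analysis.** Section 5.4 says the survey at 0, 3 and 6 months covers use of prevention services, "readiness for intervention, and injection related risk behaviors". Appendix 1, Section 1.7 names readiness to start addiction treatment as an outcome of the within-person comparison (A), and defines comparison (B) as sites with navigation against sites without. Section 6.0 (Data Analysis for Aim 3) plans generalized linear mixed growth models controlling for time-variant covariates, which it does not list.

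**The concern.** Allocation is by site, so comparison (B) depends on the two groups being alike in what they would have done without navigation. Comparison (B) is also the only comparison of the survey outcomes with contemporaneous controls: comparison (A) has no control group, and comparison (C) uses external data sources.

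Readiness for treatment and existing contact with the syringe service could both affect change over six months in treatment use, perceived access and risk behaviour. If entry procedures select differently on these features, the growth rates of the two groups can diverge with no effect of navigation, or a real effect can be hidden. Readers would be unable to tell either case from an intervention effect, because the plan does not require entry route to be recorded or baseline readiness to enter the model.

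**Working it through.** **1. The entry rules side by side**

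| Element | Intervention sites | Control sites |
|---|---|---|
| Eight-route list (Section 4.0) | Applies | Applies as written (six sites) |
| Separate entry sentence (Section 4.0) | None | Recruited at regular exchange; replacement or addition not stated |
| Peer coupon (Section 4.0) | After two attended navigation sessions | Trigger cannot occur, as no navigation is provided (Appendix 1, Section 1.4) |
| $10 peer payment (Section 9.0) | Offered | Offered as written |

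The coupon row is a definite asymmetry: a chain of peer referrals can start only from the intervention group. The second row is an ambiguity. The last two rows conflict, because a payment is offered for a referral that control participants have no described means of making.

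**2. What the planned model removes**

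Write a participant's outcome, on the link scale, as a person-specific intercept plus (slope) × (time). A fixed baseline gap between groups goes into the intercept. If readiness R also changes the slope, slope = b0 + b1·(group) + b2·R. Leaving out the R-by-time term makes the estimated group slope difference equal, approximately, to b1 + b2·(mean R in intervention − mean R in control). The second part is bias. It is zero only if mean readiness is equal or b2 = 0, and the documents support neither assumption. The same holds for syringe-service use.

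**3. The plan's own power figure**

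Inputs from Section 7.0: n1 = 135 controls, n2 = 270 intervention, p1 = 0.28, p2 = 0.42, 80% power. Section 7.0 states no alpha for Aim 3; two-sided 5% is assumed.

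- Pooled proportion = (135×0.28 + 270×0.42)/405 = 0.3733
- SE under the null = √[0.3733×0.6267×(1/135 + 1/270)] = 0.0510
- SE under the alternative = √[0.28×0.72/135 + 0.42×0.58/270] = 0.0489
- Power = Φ[(0.14 − 1.96×0.0510)/0.0489] = 79.4%

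The stated 80% is reproduced. The calculation takes any difference between groups to be due to navigation.

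**4. Illustration of the stakes (sizes assumed)**

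Use the same formula and the same outcome, with controls at 28% and no adjustment. Let d be a difference in that outcome produced by recruitment alone. A positive d favours the intervention group.

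| d (points) | Rejection rate, no navigation effect | Power, true effect 14 points |
|---|---|---|
| −10 | 63.3% | 12.7% |
| −5 | 20.1% | 43.6% |
| −2 | 7.3% | 66.5% |
| 0 | 5.0% | 79.4% |
| +2 | 6.8% | 88.7% |
| +5 | 17.2% | 96.4% |
| +10 | 51.4% | 99.7% |

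For d = +5: pooled proportion 0.3133, SEs 0.0489 and 0.0481; upper tail 1 − Φ[(1.96×0.0489 − 0.05)/0.0481] = 17.0%, lower tail 0.1%. For d = −5 with a 14-point effect, the comparison is 28% versus 37%: pooled proportion 0.34, SEs 0.0499 and 0.0485; Φ[(0.09 − 1.96×0.0499)/0.0485] = 43.6%.

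The documents do not say which row applies. Zero is among the possibilities.

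**The case against.** The strongest defence is that the entry list is common to all six sites. Most of its routes, such as HIV/HCV testing and naloxone training, require no expressed interest in navigation. The sentence about controls may simply name a point of contact. The target-population sentence in Appendix 1 is not limited to intervention sites. This stands: a reader might infer that intervention participants are help-seekers and controls ordinary exchange clients, but the documents do not support that contrast.

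A reader might also infer that the bias favours the intervention. That does not stand either. Peers who arrive by coupon did not come forward themselves and could be less ready. Flyers and Facebook could reach people with little contact with the syringe service, and these are listed for all six sites. Whether recruited peers use the service is not stated.

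The plan is also open about its limits. Appendix 1 acknowledges the biases of a non-randomized design, assigns perceived access and readiness to the within-person comparison, and uses growth models that deal with fixed baseline gaps. This is real but partial mitigation. Comparison (A) cannot separate navigation from change that would have happened anyway, and a different expected trajectory remains in (B).

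Finally, the time-variant covariates are not listed, so readiness is not expressly excluded. But no section names baseline readiness, service use or entry route as an adjustment variable, or any matching or weighting. Appendix 2 shows no readiness item, so which survey question would serve needs to be stated.

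**Conclusion.** The point holds as a risk that the plan leaves open. The coupon route starts only in the intervention group, the routes at control sites are ambiguous, and comparison (B) has no stated adjustment for the selection that could follow. There are no baseline data by group, so the documents do not show that the groups differ, by how much, or in which direction.

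The size is conditional. Under the assumptions in the working (two-sided 5%, control rate 28%, unadjusted two-proportion comparison), a 2-point recruitment difference matters little. A 5-point difference raises the false-positive rate to about 17–20%, or, if it runs against the intervention group, cuts power for the planned effect to about 44%. These figures apply to the planning outcome, the share giving the top rating for ease of access to addiction treatment. They should not be carried over to treatment initiation or other outcomes. The risk warrants a change because the remedy is cheap and the survey is already said to assess the variables.

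**What to change.** 1. **Section 6.0, Data Analysis for Aim 3.** Adjust the comparison (B) models for baseline readiness and baseline syringe-service or prevention-service use, each with its interaction with time, from the 0-month survey. Name the survey items. Where readiness is itself the outcome, handle its baseline value through the outcome model and not as an added covariate-by-time term.
2. **Entry route.** Record it for every participant (staff contact, advertisement, peer coupon) and repeat comparison (B) without peer-recruited participants. This shows whether the one-sided route drives the result; it does not correct for readiness differences within the other routes.
3. **Sections 4.0 and 9.0.** Reconcile them: state whether recruitment at regular exchange replaces or adds to the eight-route list at control sites, and whether coupons and the peer payment apply there.

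The cost is a few model terms, one data field, one sensitivity analysis with a smaller intervention group, and clarified wording. Changing notification triggers or coupon timing is not needed for this. Made during accrual, which Section 5.4 describes as running to March 2023, such a change would create early and late cohorts with different entry rules.
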